African Americans are disproportionately burdened with tobacco-related health diseases compared to other racial groups in the US^{23,24}. African Americans who smoke are more likely to develop lung cancer compared to smokers of other ethnic/racial groups^{25,26}. These health disparities exist even though African Americans are more likely to be light smokers (smoke less than 10 cigarettes per day)^{27,28} and less likely to be daily smokers^{29,30}. African Americans also take in more nicotine when smoking compared to White people who smoke³¹. The more intense smoking by African Americans may be related to the observation that 80% of African Americans who smoke are menthol smokers^{5,32}. Menthol has cooling and analgesic properties via the transient receptor potential channels^{33,34}, which may reduce irritation from tobacco smoke and nicotine^{18,35}. **Menthol cigarettes pose a greater public health risk than non-menthol cigarettes because those who use menthol cigarettes have higher nicotine dependence^{5,36-38} and decreased success in quitting smoking^{37,39}.**

It is important to understand the role of menthol flavor in nicotine dependence in African Americans. Nicotine, a compound found in tobacco products, activates nicotinic acetylcholine receptors in the mesolimbic pathway to induce rewarding and reinforcing properties⁴⁰. Constituents of tobacco products that have an influence on nicotine levels may influence dependence and addiction of tobacco products. Preclinical studies suggest that menthol inhibits nicotine metabolism⁴¹ by inhibiting the enzyme primarily responsible for the metabolism of nicotine through oxidation, CYP2A6⁴². Additionally, studies have also shown that African Americans who smoke have a slower nicotine metabolism than White people who smoke^{31,43,44}. African Americans who smoke have been shown to have slower oxidative metabolism of nicotine and slower N-glucuronidation than White people who smoke⁴⁵. However, since 80% of African Americans who smoke, smoke menthol cigarettes, it is unclear if the effect on nicotine metabolism in African Americans is the result of menthol exposure. Furthermore, there are few studies that have investigated the differential impact of menthol on nicotine metabolism within the African American population. Additionally, It has been shown that females who smoke are more likely to smoke menthol cigarettes compared to men, however gender differences within Black people who smoke is understudied⁴⁶.

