Experimental Design: Aim 1 focuses on the directed e-cigarette administration procedure. Saliva NMR will be assessed at intake appointment and will be a continuous measure in this study^{59,60}. Following overnight abstinence from combustible tobacco products (CO≤10 ppm), African Americans who smoke will participate in a double-blind, counterbalanced and randomized e-cigarette exposure laboratory study where they will receive two e-liquid flavors (menthol, tobacco) with a fixed nicotine salt concentration in e-cigarettes (5%) on two separate days (one flavor condition per session). The directed e-cigarette administration procedure will consist of 1 fixed-puffing bout (puffing bout=10 puffs, 3 sec each puff, 30 sec puff interval) as done previously by my mentor, [name]. Per the procedures conducted by my co-mentor [name] research group^{62,63}, plasma nicotine levels will be assessed at baseline and 5, 15, 30, 45 and 60 minutes after nicotine exposure via e-liquids during the directed e-cigarette administration procedure. Heart rate and blood pressure will be measured at 5, 15 and 30 minutes after the final puff. Participants will rate irritation/harshness, coolness, cigarette craving, e-cigarette craving, liking of e-cig taste, reward/appeal of e-cig, nicotine withdrawal and stimulation at baseline, 5 and 15 min after nicotine concentration exposure. Participants will be told that they can stop anytime if they feel uncomfortable. **Independent variables:** sex (male or female), nicotine metabolite ratio, flavor (menthol, tobacco), **Dependent variables:** primary outcomes- plasma nicotine boost, nicotine area under the curve; secondary outcomes- cigarette craving; exploratory outcomes- reward/appeal of e-cigs, e-cig craving, irritation/harshness, coolness, nicotine withdrawal, stimulation, liking of e-cig taste. We will explore gender differences for all outcomes.

Aim 2: Elucidate the relationship between menthol flavor (vs tobacco flavor) and NMR on nicotine pharmacokinetics and subjective effects during e-cigarette ad libitum use

Eligibility/ Recruitment/Screening: African Americans who participate in Aim 1 will participate in Aim 2.

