3. E-cig Effects (Adapted from Drug Effects Questionnaire (DEQ⁶¹)(experimental sessions): A modified version of the Drug Effects Questionnaire will be used in which participants will rate acute responses to the e-cig on a 0 to 100 mm scale, from "not at all" to "extremely." 5, 15, 30, 45, and 55 minutes after each puffing, we will assess liking/wanting of drug effects (average of "I feel good e-cig effects", "I want more of that e-cig I received", "I feel the e-cig strength" and "I like the e-cig effect"), stimulant effects (average of "I feel energized" and "I feel high"), and nicotine withdrawal (average of "I feel sleepy", "I feel angry", "I feel irritable", "I am having difficulty concentrating", "I feel restless" and "I feel hungry").

For K01 metabolism study, reward/appeal of e-cigs, nicotine withdrawal and stimulation will be assessed at baseline, 5 and 15 min after nicotine exposure during the directed puffing section of lab sessions.

4. Carbon Monoxide (CO) levels (experimental sessions): At intake we will assess recent smoking and participants with ≥ 10 ppm will be included in the study for both studies. For lab sessions for both studies, CO levels in exhaled breath will be measured using a MicroCO breath CO monitor and levels of ≤ 10 ppm will be used to ensure abstinence prior to the experimental sessions.

5. Urine Cotinine levels: At intake for both studies, urine samples will be assessed with Alere iScreen OFD Cotinine urine test to verify eligibility.

6. Salivary nicotine and cotinine levels for TCORS menthol pilot study(experimental sessions): Saliva nicotine and cotinine levels will be monitored using saliva samples obtained 10 times per session (5 min prior to and 5, 15, 30, 45, and 55 minutes after the onset of puff1, and 5, 15, 30, and 45 minutes after the onset of puff 2). To try to avoid contamination from buccal nicotine, participants will be asked to rinse their mouths prior to providing each sample. These levels will be used for correlational analyses with behavioral measures and will be determined using LC/MS techniques at the core laboratory of the YCSTP.

7. Saliva nicotine metabolite ratio or NMR (trans 3'-hydrocotinine/ cotinine) for K01 metabolism study will be assessed through Yale TCORS. To try to avoid contamination from buccal nicotine, participants will be asked to rinse their mouths prior to providing each sample

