30 healthy participants will ≥ 21 years of age; smoking menthol cigarettes/cigars/little cigars at least 5 per day, with CO levels ≥ 10 ppm and have ≥ 3 on the urine NicAlert test, willing to abstain from all combustible tobacco products 12 hrs prior to each experimental session, not currently planning to stop smoking, limited experience with e-cigs (not more than 25 times lifetime).

K01 metabolism study

Eighty-five healthy African American participants (43 female and 42 males who smoke) who are ≥ 21 years of age; able to read and write English, smoking at least 5 menthol cigarettes per day on at least 25 days or more in past month^{69,70}, CO ≥ 10 ppm and provide a semi-quantitative urine cotinine result of at least 200 ng/ml assessed with Alere iScreen OFD Cotinine, willing to abstain from tobacco and nicotine products 12 hrs. prior to each lab session, used e-cigarettes at least 10 times in the past six months, do not plan to quit e-cigarette use, not planning a smoking quit attempt ,have not stopped e-cigarette use due to COVID, willing to try e-cigarettes for the study, must report ever JUUL use and/or other nicotine salt/pod e-cigarette devices (i.e., JUUL-like), report regular menthol cigarette use

7. **Subject classification:** Check off all classifications of subjects that will be specifically recruited for enrollment in the research project. Will subjects who may require additional safeguards or other considerations be enrolled in the study? If so, identify the population of subjects requiring special safeguards and provide a justification for their involvement.

Children

Healthy

Fetal material, placenta, or dead fetus

 Non-English Speaking	 Prisoners	 Economically disadvantaged persons
 Decisionally Impaired	 Employees	 Pregnant women and/or fetuses
 Yale Students	 Females of childbearing potential	

NOTE: Is this research proposal designed to enroll children who are wards of the state as potential subjects?

Yes No

8. **Inclusion/Exclusion Criteria:** What are the criteria used to determine subject inclusion or exclusion?

CORE INCLUSION/EXCLUSION CRITERIA FOR BOTH STUDIES:

Inclusion:

- At least 21 years of age
- Able to read and write English.
- Smoking at least 5 menthol cigarettes/cigars/little cigars per day

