- Report regular menthol cigarette use
- CO \geq 10 ppm and have at least 200ng/ml urine cotinine
- Willing to abstain from combustible tobacco products 12 hrs prior to each experimental session.
- not planning a smoking quit attempt.
- Have not stopped use due to COVID.
- used e-cigarettes at least 10 times in the past six months.
- Fully vaccinated against COVID-19.

Exclusions:

- Use of psychoactive drugs including anxiolytics, antidepressants, and other psychostimulants unless prescribed and stable for two months.
- Current diagnosis of any severe psychiatric disorder
- Any significant current medical condition such as neurological, cardiovascular, endocrine, renal, pulmonary or hepatic pathology that would increase risk or would interfere with/mimic tobacco abstinence.
- Known hypersensitivity to propylene glycol and nut allergies.
- Pregnant or lactating females.
- current criteria for moderate or severe cannabis and alcohol use disorder per DSM-5 criteria.
- current criteria for other substance use disorders per DSM-5 criteria.
- Seeking treatment to stop smoking.
- individuals who do not want to use e-cigarettes.
- Uncontrolled asthma (defined as <20 on Asthma Control Test) AND/OR endorsement of "yes" to environmentally induced bronchospasm that requires prescription Epipen)
- blood pressure >170/>100 and heart rate >100
- vaping of CBD/THC or marijuana related products in the past 3 months
- For current THC vapers: Any report of mild or great EVALI-related symptoms (i.e. cough, shortness of breath, chest pain, nausea, vomiting, stomach pain, diarrhea, fever, chills, or weight loss) without non-EVALI reasonable and proximal cause

K01 metabolism study-specific inclusion criteria:

- 1) African American

- 2) must report history of JUUL and other nicotine salt/pod devices (i.e., JUUL-like)

9. How will **eligibility** be determined, and by whom?

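### The CO rule meant to confirm abstinence before each session (10 ppm or below) shares its cut-off with the intake rule for recent smoking (10 ppm or above), so entrants at about 10 to 20 ppm can pass it well short of 12 hours

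*Combined protocol and SAP*

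**What the plan says.** Item 4 of the Assessments list (Section I.4, Research Plan) sets both CO rules for both studies. The intake rule is "At intake we will assess recent smoking and participants with ≥ 10 ppm will be included in the study for both studies". The session rule is "levels of ≤ 10 ppm will be used to ensure abstinence prior to the experimental sessions". The session limit is repeated in the K01 paragraph of the Statement of Purpose (Section I.1) and in the experimental designs of the TCORS pilot and of K01 Aim 1, where the wording is "Following overnight abstinence from combustible tobacco products (CO≤10 ppm").

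The abstinence required is 12 hours. The core inclusion criteria (Section I.8) say "Willing to abstain from combustible tobacco products 12 hrs prior to each experimental session". The K01 text under Subject Population (Section I.6) is wider: "willing to abstain from tobacco and nicotine products 12 hrs. prior to each lab session".

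The minimum smoking rate is low. The core criterion is "Smoking at least 5 menthol cigarettes/cigars/little cigars per day", and for K01 it is "smoking at least 5 menthol cigarettes per day on at least 25 days or more in past month". The K01 background (Section I.3) notes that "African Americans are more likely to be light smokers (smoke less than 10 cigarettes per day").

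Other session measures bear on recent use, but none has an abstinence limit:
- the 30-day Timeline Follow Back, which is self-report (item 20);
- saliva nicotine and cotinine 5 minutes before the first exposure in the TCORS pilot, intended for correlational analyses (item 6);
- baseline plasma nicotine in K01 (item 25).

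Urine cotinine is tested at intake only (item 5).

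**The concern.** One number is used in both directions, and both limits include it. A participant who enters at 10 ppm while smoking as usual already meets the session rule. One who enters a little higher needs only a modest fall. For these people the rule does not do what item 4 says it does.

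Overnight abstinence is the common starting point of every session. It sets the level from which craving and withdrawal are relieved (secondary outcomes in the TCORS pilot; craving is secondary in K01). It also clears nicotine before the K01 primary outcomes, plasma nicotine boost and area under the curve. Item 25 says only that these two will be calculated and states no baseline correction for the area. The K01 model in Section I.13 contains NMR, time, flavor and sex, with no term for session CO or pre-session nicotine.

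In K01 each session carries one flavor, so unequal abstinence on the two days falls on the flavor contrast. In the TCORS pilot each of the first two sessions carries one nicotine form, so it falls on the form contrast. Both TCORS flavors are given within the same session, so that contrast is better protected.

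**Working it through.** The plan states no figure to reproduce. The check is one of logic, then of sensitivity to an assumed decline rate.

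**Inputs from the documents.** Intake CO at least 10 ppm; session CO at most 10 ppm; required abstinence 12 h.

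**Assumptions, not in the documents.** CO falls exponentially with half-life h, taken as 3 to 6 h and stretched to 2 to 8 h. The intake reading C0 represents the person's smoking level. The nicotine half-life is 2 h, range 1 to 3 h.

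**Step 1, overlap.** The readings that satisfy both C ≥ 10 and C ≤ 10 are the single value 10 ppm. This step needs no assumption.

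**Step 2, hours needed to pass.** t = h × log2(C0/10). For example, from 15 ppm with h = 4: 4 × log2(1.5) = 4 × 0.585 = 2.3 h.

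| Intake CO (ppm) | h = 2 | h = 3 | h = 4 | h = 6 | h = 8 |
|---|---|---|---|---|---|
| 10 | 0 | 0 | 0 | 0 | 0 |
| 12 | 0.5 | 0.8 | 1.1 | 1.6 | 2.1 |
| 15 | 1.2 | 1.8 | 2.3 | 3.5 | 4.7 |
| 20 | 2.0 | 3.0 | 4.0 | 6.0 | 8.0 |

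Allowing 2 ppm of ambient CO, t = h × log2((C0 − 2)/8). From 20 ppm this gives 2.3, 4.7, 7.0 and 9.4 h for h = 2, 4, 6 and 8. Every value is below 12 h.

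**Step 3, when the rule would need 12 hours.** C0 = 10 × 2^(12/h): 640, 160, 80, 40 and 28 ppm for h = 2, 3, 4, 6 and 8.

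**Step 4, what 12 hours would look like.** From 20 ppm, 20 × 2^(−12/h) is 1.2 ppm at h = 3 and 5.0 ppm at h = 6. A low-CO entrant who really abstained should therefore read well under 10 ppm.

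**Step 5, nicotine left.** Fraction = 2^(−t/half-life). After 3 h: 2^(−1.5) = 35% (12% to 50% over the range). After 12 h: 2^(−6) = 1.6% (0% to 6%).

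**Step 6, what a half-of-intake rule adds.** Falling to C0/2 takes h × log2(2) = h, that is 3 to 6 h. For entrants at 10 to 20 ppm, the minimum rises from between 0 and 6 h to between 3 and 6 h. Above 20 ppm, C0/2 exceeds 10, so the absolute limit already binds and nothing is added. In the hardest case for a genuine abstainer (entry at 10 ppm, limit 5 ppm), the 12-hour reading is 10 × 2^(−2) = 2.5 ppm at h = 6. With 2 ppm ambient it is 2 + 8 × 2^(−2) = 4.0 ppm at h = 6 and 2 + 8 × 2^(−1.5) = 4.8 ppm at h = 8. The person still passes.

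**The case against.** The case on the other side has several parts, and much of it stands.

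- **Only the 10 ppm overlap follows from the text.** True. The rest needs a half-life, although the conclusion is the same from 2 to 8 h.
- **A reader might infer that K01 enrolls mostly light smokers with CO near 10 ppm.** The documents do not support this. The background statement is comparative and describes a population, not the enrolled sample. The same section reports higher nicotine intake in this group, and entry also requires 25 smoking days in the month and urine cotinine of at least 200 ng/ml. Low intake values are possible; how common they will be is unknown.
- **A reader might infer that the flavor or form effects will be biased.** The documents do not support this either. Both studies are randomized, double-blind crossovers, and nothing suggests that lapses would follow the assigned condition. The expected result is extra variability, which has not been quantified.
- **Better markers are already collected.** True. Pre-exposure plasma or saliva nicotine measures the harm more directly. It can also reflect e-cigarette use, which CO, as a marker of combustible smoking, would not check; this matters in K01, whose participants use e-cigarettes. But no rule in the plan uses these samples to judge abstinence.
- **Halving CO does not prove 12 hours either.** True, as Step 6 shows. It also rests on a single intake reading whose timing after the last cigarette is not specified.

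**Conclusion.** The point holds in a limited form. The two rules overlap at 10 ppm, and under an assumed CO half-life of 3 to 6 h an entrant at 12 to 20 ppm can pass after about 0.8 to 6 h instead of 12. The session check therefore cannot bear the weight item 4 gives it for entrants in that range.

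It would go too far to call the check empty. Someone who enters well above 10 ppm must show a real fall, though not necessarily one that takes 12 hours. The share affected cannot be computed, and the likely consequence is noise in the K01 flavor contrast and the TCORS form contrast. It is worth correcting because the correction is cheap, not because the design fails without it. The stated K01 power figures were not tested here.

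**What to change.** 1. In item 4, and in the three other places that state the session limit (Statement of Purpose for K01, TCORS experimental design, K01 Aim 1 experimental design), require session CO **below** 10 ppm **and** no more than half of the participant's own intake CO. Describe this as a stricter check that helps entrants at about 10 to 20 ppm, not as confirmation of 12 hours.
2. State what happens when a session reading fails. No such procedure is written now; the one rescheduling allowance found concerns a positive drug screen at intake.
3. Pre-specify a sensitivity analysis for the between-session contrasts that excludes sessions failing the relative CO criterion or showing raised pre-exposure nicotine (K01 baseline plasma; TCORS saliva 5 minutes before the first exposure). Fix the nicotine threshold before unblinding. Keep the planned intent-to-treat analysis as the main one.
4. Reconcile the scope of abstinence: the core criteria name combustible tobacco, while the K01 population text adds nicotine products.

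Cost: no new measurement, since intake CO, session CO and pre-exposure nicotine are already collected. Some sessions would be rescheduled; how many cannot be estimated without the intake CO distribution. The extra analysis is small.

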glycerin concentrations that are available in e-liquids on the market. Some research has indicated that in large doses propylene glycol and vegetable glycerin can be harmful. Little is known about the short or long-term effects of inhaling flavorants. However, the participants will be allowed to stop the session at any point if they experience any side effect. Research staff will monitor e-cigarette use during the lab session. Participants who report recent THC vaping (within the last 90 days) will be monitored for EVALI symptoms, which are currently evaluated on our Health Assessment Checklist. Specifically, if a participant indicates EVALI symptoms (i.e. cough, shortness of breath, chest pain, nausea, vomiting, stomach pain, diarrhea, fever, chills, or weight loss), the researcher will assess if the symptom is related and proximal to a non-EVALI cause (e.g. Nausea/vomiting related to food poisoning, Shortness of breath related to seasonal allergies). If a reasonable & proximal cause is identified, participant will continue with session. If not, participation will be deemed ineligible (if identified at intake) or withdrawn (at lab sessions). We will consult with study pulmonologist for any cases in which the etiology of symptoms is not apparent or is unclear. Additionally, lung spirometry readings are already assessed intake. Participants who report THC vaping will receive education material about EVALI from <https://www.yalemedicine.org/conditions/evali>. All participants will have a physical exam(i.e. review of medical history, heart rate, blood pressure, lung spirometry, pulse oximetry) and be deemed healthy prior to participation and will continue to monitor their health closely during the study. Participants will be informed that if they experience any symptoms (cough, shortness of breath, chest pain, nausea, vomiting, stomach pain, diarrhea, fever, chills, or weight loss) or have other concerns, that they should let us know and also let their doctor know right away. Any participants reporting mild or moderate respiratory symptoms will be referred to their primary care physician or will be referred to care. They will be informed to the emergency room right away if their symptoms are severe increase rapidly. It is possible that the hospital may report cases of illness after using e-cigarettes to the State Health Department and the CDC. The report will contain the name and address of the person who is ill. Given the risk of THC vaping and EVALI, participants who report THC vaping and have endorsement of these symptoms at baseline without reasonable and proximal cause will be ineligible. If these participants develop symptoms during the study without reasonable and proximal cause, they will be withdrawn, referred to their primary care physician, or other care as needed.

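### Section I.8 excludes anyone who vaped THC in the past 3 months, but its next bullet and Section I.10 imply that such a person may enrol unless symptoms are unexplained

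*Combined protocol and SAP*

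**What the plan says.** Section I.8 opens its list under the title "CORE INCLUSION/EXCLUSION CRITERIA FOR BOTH STUDIES", so what follows binds both the TCORS pilot and the K01 study. Two adjacent exclusion bullets deal with cannabis vaping:

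- The first excludes "vaping of CBD/THC or marijuana related products in the past 3 months". It carries no symptom condition.
- The second begins "For current THC vapers: Any report of mild or great EVALI-related symptoms" and is qualified so that symptoms with a credible non-EVALI explanation do not count.

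Section I.10 (Risks), in the paragraph on propylene glycol and vegetable glycerin, sets out a procedure for the same group:

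- "Participants who report recent THC vaping (within the last 90 days) will be monitored for EVALI symptoms".
- When such a person reports symptoms: "If a reasonable & proximal cause is identified, participant will continue with session".
- When no such cause is found: "If not, participation will be deemed ineligible (if identified at intake) or withdrawn (at lab sessions".
- Later in the paragraph: "participants who report THC vaping and have endorsement of these symptoms at baseline without reasonable and proximal cause will be ineligible".
- For the period after entry: "If these participants develop symptoms during the study without reasonable and proximal cause, they will be withdrawn".

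Neither section refers to the other on this point.

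**The concern.** The first bullet makes recent THC vaping disqualifying in itself. The second bullet and Section I.10 make it a reason to ask about symptoms, and only unexplained symptoms disqualify. A screener holding both texts can defend either decision for the same applicant.

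What is at stake is who receives study product in a group that the protocol itself singles out for EVALI risk. Participants use e-cigarettes at three sessions in the TCORS pilot and two in the K01 study. K01 recruitment is planned over five years, so staff could apply different rules at different times without anyone departing from the written protocol.

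**Working it through.** No sample size, power or event figure bears on this point, so the check is to apply each text to the same applicants. The look-back windows do not separate the rules: 3 months in Section I.8 and 90 days in Section I.10 are in practice the same period.

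Take an applicant who vaped THC 30 days before intake and meets every other criterion.

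| Applicant | Section I.8, first bullet | Section I.8, second bullet, and Section I.10 |
|---|---|---|
| (a) No EVALI-type symptoms | Excluded | Not made ineligible; monitored |
| (b) Symptoms with an accepted non-EVALI cause | Excluded | Not made ineligible; continues |
| (c) Symptoms without such a cause | Excluded | Ineligible at intake |

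The texts agree on (c) and diverge on (a) and (b).

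Two further cases mark the limits of the conflict:

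- **THC vaping only, more than 3 months ago.** The first bullet does not reach this person. The sentences in Section I.10 on baseline ineligibility and later withdrawal carry no time window and can apply. There is no conflict here, and this is one legitimate use for the Section I.10 rule.
- **CBD-only vaping within 3 months.** The first bullet excludes this person. The second bullet and the eligibility rule in Section I.10 speak only of THC, so nothing opposes the exclusion.

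Next, can the texts be reconciled as written?

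1. *Read the exclusions as cumulative.* Section I.8 then gives one answer: excluded. But anyone who currently vapes THC has, on an ordinary reading, done so within 3 months, so the second bullet is left with nothing to do. The intake rule in Section I.10 for people reporting use within 90 days is likewise left without an eligible subject.
2. *Read Section I.10 as covering only vaping that begins or comes to light after enrolment.* The text does not allow this. It states what happens if the problem is identified at intake, and it states a baseline ineligibility rule. Both turn on symptoms, which would be irrelevant if recent use were already disqualifying.

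Neither reading accommodates all the sentences.

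**The case against.** The best defence is that Section I.8 is where eligibility is defined, while Section I.10 describes risks. Exclusion bullets add to one another, and a redundant bullet does not repeal the one above it. Nor does Section I.10 ever say outright that a symptom-free recent THC vaper is eligible; it gives a condition sufficient for ineligibility and a monitoring procedure. All of this is fair. It means that enrollability under Section I.10 is implied, not declared, and that Section I.8 is the natural text to let prevail. It does not explain why an intake rule for 90-day users should depend on symptoms, and the protocol does not state that Section I.8 controls.

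It is also fair that the consequence is limited. The Safety Monitoring Plan in Section I.12 has symptoms, including EVALI symptoms, monitored in all participants, with study physician review, attribution and grading of adverse events, and investigator authority to end participation. Spirometry is done at intake and pulse oximetry at in-person visits. A reader might infer that recent THC vapers would be unprotected if enrolled; the documents do not support that. Monitoring, however, does not tell staff whether the person may enter.

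Other stronger readings also fail:

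- A reader might infer that CBD-only vapers lose their exclusion if Section I.10 prevails. Its eligibility rule concerns THC and displaces nothing on CBD.
- A reader might infer that every THC vaper without unexplained symptoms would be exposed under Section I.10. Each must still meet all the other criteria, and the plan expects attrition between intake and the sessions.
- A reader might read the provision of EVALI education material as proof of enrolment. The protocol also calls people at intake participants, so that sentence proves nothing either way.

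**Conclusion.** The inconsistency is real and confined. For a THC vaper within the past 3 months who has no symptoms, or has explained ones, Section I.8's first bullet says excluded; the next bullet and Section I.10 imply enrollable; and no text ranks them. This rests on the wording alone and on treating 3 months and 90 days as the same window.

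Its size in people cannot be given. Section III.1 plans 60 + 23 × 5 = 175 initial appointments across the two studies, and it is tempting to multiply that by a share of recent THC vapers. The documents give no such share. Moreover, Section III.6 schedules intake after screening has found the person eligible, so some or all of this group may already have been removed.

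No outcome, power statement or analysis is affected. The point is one of safety and consistent enrolment. It merits a wording amendment because the group is one the protocol treats as being at higher risk.

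**What to change.** Keep the 3-month CBD/THC exclusion in Section I.8 as the controlling rule and say so. It is already written there, and no stated aim needs recent THC vapers. Then:

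- delete the bullet on current THC vapers, or reword it so that it no longer suggests they can qualify;
- limit the symptom and withdrawal rule in Section I.10 to participants whose THC vaping was more than 3 months ago, or who start or first disclose THC vaping after enrolment;
- align the screening form with the amended text.

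The cost is a wording amendment with no new procedure, plus the loss of any recent THC vapers now being admitted under Section I.10.

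If the investigators and the IRB do intend to enrol recent THC vapers, the unconditional THC exclusion should instead be removed explicitly, CBD vaping kept as an exclusion, and the Section I.10 rule retained. That choice accepts their exposure to study product under the existing monitoring.
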